12. DATA HANDLING AND RECORD KEEPING

13. FINANCING AND INSURANCE

14. PUBLICATION POLICY

15. BIBLIOGRAPHY

1. INTRODUCTION

Telomere biology is a growing research field. New genes and/or genomic variants of established telomere-related genes are still being identified as modulators of telomere length. While long telomeres are considered as a sign of good cellular health associated with a better regenerative potential of the tissues, abnormally short telomeres are responsible for premature ageing syndromes, collectively known as telomeropathies, that can be very severe and life threatening. The diagnosis of telomeropathy is complicated by the fact that patients can present with a variety of symptoms at various ages, including aplastic anemia, pulmonary fibrosis, liver cirrhosis, unexplained liver regenerative nodular hyperplasia or myelodysplasia. If, to date, there is no treatment yet to these genetic diseases, identifying the telomeric origin of the disease is important to avoid inappropriate therapeutic treatments. Developing new and poorly invasive diagnostic tools for telomeropathy is one of our research objectives. Our second objective is to better understand the genetics of telomeropathies through functional studies of new disease-causing mutations. Together, these two objectives will contribute to a better detection and understanding of telomere-associated pathologies.

TELOMEROPATHIES: DIAGNOSIS

Telomeropathies are premature ageing diseases resulting from pathogenic germline mutations in telomere biology-related genes. Most telomeropathy patients have telomeres that are too short for their age. Telomere length (TL) can be measured in blood cells using a technique called Flow-FISH (FF) that combines fluorescent in situ hybridization (FISH) with flow cytometry (Baerlocher et al. 2006). To provide a diagnostic tool for telomeropathies in Belgium, the laboratory of [name], in collaboration with CUSL, recently implemented the FF technique and measured TL in a cohort of 491 healthy volunteers aged 0-99 years. In combination with FF, additional genetic and phenotypic studies on patients' cells are needed to tell whether the disease is caused by prematurely defective telomeres. Knowing this is important to i) exclude any other cause of the disease, ii) avoid the use of inappropriate treatments, iii) better manage the immunosuppressive regimens that are associated with hematopoietic stem cell or lung transplantation in some telomeropathy patients and iv) enable possible targeted therapies. For instance, while pulmonary fibrosis carriers with TOLLIP polymorphism may benefit from N-acetylcysteine treatment, those with defective telomeres may possibly benefit from Danazol, a telomerase-activating drug previously associated with increased TL in PBMCs and stability of lung function in idiopathic PF (IPF) patients (Townsley et al. 2016).

To date, mutations in 15 telomere biology-related genes have been linked to telomeropathies and include *TERC* and *TERT* telomerase core components, various chaperone genes with roles in *TERC* maturation and stability, shelterin complex genes, the CST complex with important function in telomere replication and *RTEL1* with multiple roles at telomeres, including replication (Savage 2018). There are however many patients with abnormally short telomeres and still unidentified mutation. On the other hand, in patients with *CTC1* or *POT1* mutations, presenting with severe telomeropathies, telomeres

are defective but not abnormally shortened (Gu et al. 2018), underlying the need to combine TL measurements with additional phenotypic and genetic analyses for the proper diagnosis of telomeropathies.

One way to evaluate telomere dysfunction, independently of TL measurement in blood cells by FF, is to perform a combination of telomeric FISH and immunofluorescence (FISH/IF) against DNA damage markers to guantify the damaged telomeres, a conserved feature of cells from telomeropathy patients. The evaluation of cellular senescence, using the well-established Senescence-Associated β -Galactosidase (SA- β -Gal) assay (Dimri et al. 1995) is vet another assay to evaluate a premature ageing cellular phenotype. Importantly however, neither FISH/IF nor SA-β-Gal assays can be performed on blood cells. The cellular diagnosis therefore requires other cell types. Usually, a skin biopsy is performed that requires to establish a primary culture of fibroblasts for further analyses. The skin biopsy is however invasive, leaving permanent scars. A skin biopsy can also be used to identify the genetic mutations at the origin of the disease. This type of cell is usually preferred over blood cells because of the known ability of blood cells to undergo somatic genetic rescue that can offset the pathogenic effect of germline mutations (Revy et al. 2019). In this respect, although intragenic compensatory mutations are observed in blood cells from telomeropathy patients, in the majority of the cases, indirect somatic genetic rescue is obtained through the acquisition of well-defined activating point mutations in the promoter of hTERT gene that codes for the catalytic subunit of telomerase (Revy et al. 2019). Since this has already been observed in cases of heterozygous germline mutations in PARN, NHP2 or TERC genes (all involved in maturation and activity of telomerase), this suggests that the detection of these point mutations in blood cells may be a strong indicator of the existence of a telomeropathy, prior to the exome-seg analysis.

Importantly as well, having non-blood cells in culture, like fibroblasts, allows functional studies of the mutations to increase our knowledge of the telomeropathies at the cellular level.

Altogether, this underlines the interest of having access to non-blood cells from telomeropathy patients for proper diagnosis, mutation identification and functional studies. In that context, developing alternative and less invasive approaches to collect non-blood cells so as to replace skin biopsies would be highly beneficial to patients.

THE OLFACTORY EPITHELIUM: AN ALTERNATIVE SOURCE OF CELLS FOR TELOMEROPATHY DIAGNOSIS AND UNDERSTANDING?

The olfactory neuroeptithelium (ONE), located at the upper part of nasal fossae in a region named the olfactory cleft, is considered as a unique structure owing to its sustained regenerative capacity. Indeed, mature olfactory sensory neurons are continuously produced from a population of stem cells (horizontal and globose cells) throughout adulthood age (Rawson and Ozdener 2013). Consequently, ONE is considered as the unique source of regenerating neuronal cells that can be easily obtained from living humans. ONE cells can be easily collected using a technique called nasal brushing. In this technique, ONE is sampled using a cytology brush that is introduced in the olfactory cleft at the level of the head of the middle turbinate and gently moved by circular movements to collect epithelial cells. It can easily be performed under endoscopic control and has no known adverse effect (Benitez-King et al. 2011; Orru et al. 2014). This non-invasive technique was found to be efficient in obtaining mature olfactory sensory neurons as well as neuronal cell precursors and stem cells from healthy subjects and patients (Benitez-King et al. 2011). Importantly, neuronal precursors can be propagated in culture (Benitez-King et al. 2011). Studies have shown that the collected neuronal precursors possess an undifferentiated state, the capability of self-renewal and the capacity to proliferate and differentiate into neuronal and glial cells without genetic reprogramming (Idotta et al. 2019; Jimenez-Vaca et al. 2018; Matigian et al. 2010; McCurdy et al. 2006). Moreover, despite a superficial exfoliation, it is important to mention that nasal brushing allows the collection of a significant number of cells, Brozzetti et al. reporting that the number of cells ranged up to 2 millions, with 40% of those being neuronal cells (Brozzetti et al. 2020). Although non-invasive, the brushing technique thus represents a valuable tool to collect cells from the ONE and is thought to be an excellent surrogate model to study pathophysiological neural mechanisms.

Besides that, it is also important to underline the link between aging and dysfunction of the olfactory system. Indeed, from a behavioral point of view, it is well known that aging is associated to a progressive impairment of olfactory function (Huart et al. 2013). Although the decrease of olfaction is physiological with age, aged people having a more severe olfactory dysfunction are at higher risk to develop neurodegenerative disease, such as Alzheimer's and Parkinson's disease (Mesholam et al. 1998), and are also at higher risk of 5vears mortality (Devanand et al. 2015; Pinto et al. 2014). This relationship being specific to the sense of smell, these findings suggest that the olfactory system is particularly sensitive to aging. Currently, olfactory impairment is thus considered as an emerging biomarker of biological aging. Among the diverse hypotheses explaining the link between olfactory impairment and aging, it has been postulated that olfactory impairment might reflect a decline of this continuous neurogenesis, through environmental exposure or brain aging. Loss of this necessary process could be seen more globally as an indicator of lowered physiologic repair function which may reflect senescence.

Therefore, we think that ONE could provide an interesting cellular model for the diagnosis and study of telomeropathies and replace the invasive skin biopsies that are currently being performed for genetic and phenotypic analyses of telomere dysfunction and senescence. Moreover, assessment of olfactory function in patients with telomeropathy could bring new interesting insights.

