2. OUTLINE OF OBJECTIVES AND PROJECT DESIGN

2.1 OBJECTIVES

The main objective of this study is to develop new tools for the diagnosis and understanding of telomeropathies. Our more specific aims are:

- To assess the suitability of nasal brushing analyses and blood tests for the diagnosis of telomeropathies
- To assess whether primary cell cultures obtained from nasal brushing could constitute a valuable tool for functional studies of new germline mutations

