2.2.2 Study endpoints

Endpoint #1: To assess the suitability of nasal brushing analyses and blood tests for the diagnosis of telomeropathies.

Rationale

To date, the complete diagnosis of telomeropathies, including the identification of responsible mutations, is based on blood samples and fibroblast cultures obtained through skin biopsies. Cells obtained through nasal brushing offer the opportunity to detect mutations involved in telomeropathies, in a mildly invasive way. We will thus assess a population of patients with a suspicion of telomeropathy, using a combination of blood tests and nasal brushings, and will compare their nasal brushing results to those of age-matched healthy controls. If we confirm that the nasal brushing offers the opportunity to i) detect damaged telomeres and premature cellular senescence and ii) identify mutations related to telomeropathies, this technique could become a non-invasive clinical tool for the diagnosis work-up of telomeropathies

Assessments

We will collect blood samples in each patient and will perform a nasal brushing to each subject (patients and controls) included in this study. One sample of blood will be collected for each patient and processed following the protocol further described (see chapter 3.1.).

For nasal brushing, one collection will be performed in the most accessible nostril. We will evaluate if it is possible to detect damaged telomeres and premature cellular senescence in patient, in comparison to healthy controls.

In the patients group, collected cells will be split into three parts, two will be devoted to Endpoint#1, and the other for the Endpoint #2, following the protocol further described (see chapter 3.2.).

For patients recruited from the pediatric consultation, if possible, this sample will be collected during another medical procedure planned under general anesthesia (eg. marrow puncture). Similarly, pediatric controls will be recruited among patients undergoing elective otorhinolaryngological surgery (eg. grommets, tonsillectomy).

Endpoint #2: To develop primary cell cultures for the functional study of new germline mutations.

Rationale

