To date, various germline mutations have already been identified in telomeropathy patients, in a total of 15 genes. Understanding how these mutations were affecting telomere biology relied on *in vitro* studies with either patient-derived fibroblasts or engineered human cell lines recapitulating the mutation. This was a mandatory step towards the molecular understanding of these pathologies. Because olfactory neural precursors have the capacity to grow in culture, this offers the additional possibility to perform functional studies on primary cultures of nasal brushing-derived cells for novel mutations, with still unknown impact on telomeres, that would be identified. Again, this could advantageously replace patients' fibroblast cultures.

Assessments

The second part of cells harvested from the olfactory epithelium will be cultured, according to protocol described in chapter 3.2.

Endpoint #3: To evaluate whether patients with telomeropathies have impaired olfactory function.

Rationale

Olfactory function is decreased in several diseases and is increasingly recognized as an indicator of biological aging. To date, no data exist regarding the impact of telomeropathies on olfactory function. Therefore, we aim to psychophysically assess olfactory function in patients with telomeropathies, in comparison to age-matched healthy controls. This study will be performed in a subset of subjects (see section 7.1).

Assessment

For each participant older than 6 years old, olfactory function will be assessed with the validated test.

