13. FINANCING AND INSURANCE

The study will be funded by grants obtained by Prof. [name] and Prof. [name].

Blood sample analysis and genetic analysis (whole-exome sequencing) will only be performed in patients. For patients involved in the current study, Flow-Fish analysis is already performed in clinical routine as standard of care procedure. Similarly, genetic analysis on cellular material is considered as a standard of care for patients with suspicion of telomeropathy. Therefore, these analyses will not be associated to additional costs, neither in term of material of personal.

Indemnity for negligent and non-negligent harm will be provided by a specific insurance provided by the Cliniques universitaires Saint-Luc. Company:

Police number:

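### Nasal brushing is presented as a possible replacement for skin biopsy, but no within-patient comparison with an existing genotype or fibroblast result is planned

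*Combined protocol and SAP*

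**What the plan says.** **Purpose.** Section 1 (Introduction) proposes that olfactory epithelium could "replace the invasive skin biopsies that are currently being performed for genetic and phenotypic analyses of telomere dysfunction and senescence". The rationale for Endpoint #2 (Section 2.2.2) says of nasal cultures that "this could advantageously replace patients' fibroblast cultures". The formal aim in Section 2.1 is narrower: "To assess the suitability of nasal brushing analyses and blood tests for the diagnosis of telomeropathies".

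**Current method.** Section 2.2.2 states that the complete diagnosis "is based on blood samples and fibroblast cultures obtained through skin biopsies". The Introduction describes general practice: "Usually, a skin biopsy is performed that requires to establish a primary culture of fibroblasts for further analyses". Section 13 adds that "genetic analysis on cellular material is considered as a standard of care for patients with suspicion of telomeropathy", without naming the cell type.

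**Comparison planned.** Under Endpoint #1 the investigators "will compare their nasal brushing results to those of age-matched healthy controls". The assessment paragraph repeats the contrast: the question is whether brushing can "detect damaged telomeres and premature cellular senescence in patient, in comparison to healthy controls".

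**What is collected and analysed.** Patients give blood and a nasal brushing; controls give a nasal brushing only. Part of the patient material is frozen for exome sequencing, to be done once the suspected diagnosis is confirmed (Section 3.2). The confirming method is not stated, and neither is any comparison with another genotype. Section 9 (Data analysis) names laboratories and the Flow-FISH assay and no statistical comparison. The procedures, eligibility criteria and data analysis section mention no fibroblast sample and no retrieval of an existing fibroblast or genetic result.

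**The concern.** To judge whether a new sample type is suitable for diagnosis, its result must at some point be set against a reference in the same person. Section 2.2.2 names the reference (blood plus fibroblast culture) and then compares nasal results with a different group of people. It also says that brushing could become a clinical tool if it detects damage and senescence and identifies mutations; agreement with the existing work-up is not part of that condition.

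At stake is what may be concluded at the end. A clear patient-control difference and a list of mutations found in nasal cells could be read as support for dropping the biopsy, although the study would hold no evidence on how often the two sources agree in one patient.

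**Working it through.** **1. The plan's own figure.** Section 2.2 gives 150 patients + 100 controls = 250. The sum is right. No alpha, power, effect size or SD is given, so the number cannot be reproduced further. No figure in the plan is disputed here.

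**2. What the patient-control contrast can show.** Assume two-sided alpha 0.05, normal data and equal variances (none of these is in the documents). The detectable standardised difference is

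d = (z₀.₉₇₅ + z_power) × √(1/100 + 1/150), where √(1/100 + 1/150) = 0.1291.

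- 80% power: d = (1.960 + 0.842) × 0.1291 = 0.36
- 90% power: d = (1.960 + 1.282) × 0.1291 = 0.42

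The matching area under the ROC curve is Φ(d/√2): 0.60 for d = 0.36 and 0.62 for d = 0.42. A difference that this sample would probably find significant is therefore compatible with weak separation of individuals. Whatever its size, it carries no information on agreement with fibroblasts.

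**3. What nasal exome sequencing can show.** This is a per-patient result, not a group contrast. Without a reference genotype, however, a mutation missed in nasal cells cannot be told from one that is not there to be found. The Introduction itself notes many patients with abnormally short telomeres and no identified mutation, so a negative nasal exome is uninterpretable on its own.

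**4. What a paired analysis would add.** Neither the number of pairs nor the agreement is in the documents, so both are varied. The exact (Clopper-Pearson) 95% limits for x agreeing pairs out of n are Beta⁻¹(0.025; x, n−x+1) and Beta⁻¹(0.975; x+1, n−x).

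| Pairs | Agreeing | Observed | Exact 95% CI |
|---|---|---|---|
| 30 | 24 | 80% | 61.4% to 92.3% |
| 30 | 27 | 90% | 73.5% to 97.9% |
| 60 | 54 | 90% | 79.5% to 96.2% |
| 100 | 90 | 90% | 82.4% to 95.1% |
| 150 (every patient) | 135 | 90% | 84.0% to 94.3% |

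**5. Why overall agreement is not enough.** Patients with an existing result may be mostly positive. Suppose, for illustration, 25 of 30 pairs are reference-positive and 5 reference-negative. A nasal reading that was always positive would agree in 25/30 = 83% while being wrong in all 5 negatives. Even if all 5 negatives agreed, the exact lower limit would be 0.025^(1/5) = 0.48. Positive and negative agreement need separate lines.

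**The case against.** The strongest reply is that this is early development work: showing that a new sample type carries any disease signal properly comes before a paired accuracy study. Three stronger readings that a reader might infer also fail on the documents.

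- *That the study's stated aim is to replace biopsy.* Replacement appears in the background and rationale, worded as a possibility. The formal aim in Section 2.1 is suitability for diagnosis.
- *That routine fibroblast results already exist for enrolled patients.* No section says so. The remark that a biopsy is usually done describes general practice, and many participants are recruited on suspicion alone. Section 13 speaks only of cellular material, a term that Sections 3.2 and 9 use for nasal brushings. Nothing says that fibroblast FISH/IF or SA-β-Gal is routine at this hospital.
- *That the study can show only average differences.* Exome sequencing gives individual results, and Endpoint #2 asks whether patients' nasal cells can be cultured.

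It is also fair that intervals like those above, from a clinically selected subset, would not by themselves justify replacing biopsy. Nor are the stainings like for like: nasal cells are read from a Cytospin fraction, whereas fibroblasts must first be cultured.

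All of this limits the point without removing it. Suitability for diagnosis still needs a reference, and none is used. A paired check is plausible without any new procedure, because confirmed cases are eligible (Sections 2.2.1 and 7.1) and genetic analysis is called standard of care (Section 13).

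**Conclusion.** The point holds as a gap between the comparison planned and the use foreseen. As written, Endpoint #1 can show whether nasal staining differs between patients and controls and whether mutations can be found in nasal cells. It cannot show that nasal cells give the same answer as the current work-up in the same patient, so a statement that brushing can stand in for biopsy would be unsupported.

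The size cannot be fixed from the documents. It depends on how many patients have an existing genotype or fibroblast result, which is an assumption throughout. With 30 pairs and 90% agreement the lower limit is about 73%; with all 150 it would be 84%. The study need not be redesigned: this is an inexpensive improvement, and where it proves impossible the remedy is a narrower conclusion.

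**What to change.** Add to Endpoint #1 a prespecified paired analysis:

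- **Who.** Every patient who already has a clinical genotype or a routine fibroblast result, within the consent given. No new biopsies.
- **Mutation.** Concordance between nasal exome and existing genotype, with exact 95% CI. Record which tissue gave the existing genotype, since the Introduction notes that blood cells can acquire compensatory mutations.
- **Phenotype.** Paired agreement on damaged telomeres (FISH/IF) and SA-β-Gal, only where fibroblast results exist. A positivity cut-off must be set beforehand, as the plan gives none.
- **Reading.** Nasal readers unaware of the reference result.
- **Reporting.** The number of pairs out of the patients enrolled, and positive and negative agreement separately with exact 95% CIs.
- **Fallback.** If too few pairs exist, limit the conclusion to feasibility, mutation detection in nasal cells and patient-control differences, and make no statement that brushing can replace biopsy.

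Cost: data extraction and one table, possibly with a consent or ethics amendment, since patients may decline genetic testing (Section 5). The subset may be small and clinically selected, and Cytospin and cultured-fibroblast readings are not fully comparable; both limits should be stated with the result.

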2. OUTLINE OF OBJECTIVES AND PROJECT DESIGN

2.1 OBJECTIVES

The main objective of this study is to develop new tools for the diagnosis and understanding of telomeropathies. Our more specific aims are:

- To assess the suitability of nasal brushing analyses and blood tests for the diagnosis of telomeropathies
- To assess whether primary cell cultures obtained from nasal brushing could constitute a valuable tool for functional studies of new germline mutations

